### 5.1 Blinding and Randomization

Participants will be randomized to either CLEAR therapy or placebo at a ratio of 1 to 1 stratifying by site and use of prednisone  $\geq 10$  mg or not and using a permuted-block randomization algorithm with random block sizes. Randomization schedules will be generated by a statistician who is not involved with the conduct of the clinical trial. The Vanderbilt Investigational Pharmacy will provide each site with the study drugs and site-specific treatment assignments. The placebos and colored capsules will be obtained by each site. Pills of identical appearance containing antibiotics (each a different color) or placebo will be prepared and dispensed by each site's study pharmacy. A participant's treatment assignment will only be revealed outside the pharmacy if a clinical emergency necessitates unblinding their treatment or if requested by the DSMB. Neither participants, clinical providers, nor those influencing recruitment decisions or interpretation of data will be aware of the treatment that is assigned or the order that treatments will be allocated.

Patients will be considered enrolled upon randomization. Patients receiving any amount of study drug will be considered treated. Patients discontinued from receipt of study drug for any reason, will continue to follow all other protocol requirements for the entire 180 day study period to the extent that the informed consent is still active.

Only the investigational pharmacists and the DSMB will be unblinded to randomization assignments. There are safety issues associated the CLEAR regimen; for example, levaquin and prolongation of the QT interval. If there is a significant safety issue thought related to study drug, all four study drugs within the regimen should be stopped and the patient followed until stabilization or resolution of this issue. Efforts will be made to unblind only individuals not associated with the research and who need to know, such as an attending physician. Should un-blinding of an individual become necessary during the study, the investigator at the clinical site should contact the Vanderbilt Clinical Coordinating Center (CCC) for approval and specific unblinding instructions.

Matching placebo will be provided for each of the CLEAR therapies. At the site, only the unblinded pharmacist should know the randomization assignment for an individual patient. Riboflavin will be added to the placebos for Rifampin and Rifabutin to assure participants are not unblinded due to lack of discoloration of urine, tears.

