## 7.2 Randomization

Participants will be randomized to either CLEAR therapy or placebo at a ratio of 1 to 1 stratifying by site and use of prednisone  $\geq 10$  mg or not and using a permuted-block randomization algorithm with random block sizes. Treatment assignments of the study will be made using separate randomization schedules for each of the three participating sites. The randomization schedule will be prepared by the DCC prior to initiation of patient recruitment. Randomization schedules will be generated by a statistician who is not involved with the conduct of the clinical trial. All randomization schedules will be generated using R, will remain confidential and known only by the site pharmacists until the database is locked and randomization assignments no longer must be blinded. Randomization marks the patient's official entry into the Study. Once a participant has been started on the assigned study treatment, efforts will be made to conduct all evaluations irrespective of whether the participants complete the study treatment regimen or not, or how well the participants complies with the study treatment regimen. These efforts should continue until termination of the study. Data collections will continue even if medication must be stopped.

For the intention to treat analysis, participants will be considered treated when the first study drug is taken, regardless of the amount of study drug they receive. Participants discontinued from receipt of

study drug for any reason, will continue to follow all other protocol requirements for the entire study period to the extent that the informed consent is still active.

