## 8.2 Site Monitoring

Sites will be monitored on a regular basis by the Clinical Coordinating Center (CCC), to ensure that all regulatory requirements are met and to monitor the quality of the data collected. Records of Institutional Review Board approvals will be faxed or sent electronically to the CCC. REDCap database automated range checking may be utilized to alert data entry personnel when data out of range is entered. Data quality assurance checks will be performed to assure the data are as accurate as possible prior to locking the database. If erroneous or inappropriately missing data are noted from any one site, the CCC will develop a corrective action plan for the site(s) involved.

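### Section 5.1 asks for CCC approval before any individual unblinding and gives no emergency route to the site pharmacist, who holds the code

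*Combined protocol and SAP*

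**What the plan says.** Section 5.1 of the combined protocol and SAP has four statements that bear on unblinding an individual.

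- On when the code may be opened, a participant's "treatment assignment will only be revealed outside the pharmacy if a clinical emergency necessitates unblinding their treatment", or at the DSMB's request. This sentence names no approval step.
- On who holds the code: "Only the investigational pharmacists and the DSMB will be unblinded to randomization assignments". A later paragraph adds: "At the site, only the unblinded pharmacist should know the randomization assignment for an individual patient".
- On who should learn the result: "Efforts will be made to unblind only individuals not associated with the research and who need to know". An attending physician is the example given.
- On procedure, once unblinding of an individual becomes necessary, "the investigator at the clinical site should contact the Vanderbilt Clinical Coordinating Center (CCC) for approval and specific unblinding instructions".

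Section 7.2 says of the randomization schedules that they "will remain confidential and known only by the site pharmacists until the database is locked".

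Section 5.1 also directs that all four drugs be stopped for a significant safety issue thought to be drug-related. It does not make this depend on a code break or on the CCC.

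**The concern.** The sentence on emergencies and the sentence on procedure do not fit together. The first treats an emergency as sufficient reason to release the assignment. The second puts a request and an approval in front of every individual release. What is sought is approval, not notification, so the CCC may decline or be out of reach. Meanwhile the person who can answer is the pharmacist at the participant's own site.

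At stake is the time until a treating physician knows what the participant has taken. Stopping the capsules does not answer that question, because exposure outlasts the last dose. The protocol gives a terminal half-life of 68 hours for azithromycin (5.2.3) and a mean of 45 hours for rifabutin (5.2.4b). It describes rifampin as a potent inducer of cytochrome P450 (Section 5) and lists Torsades de Pointes among the rare reactions to levaquin (5.2.1). The protocol itself foresees emergencies in which the assignment is needed, so it should give a route that works in them.

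**Working it through.** No arithmetic applies: the protocol states no figure on this point. The check is a comparison of the passages.

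1. **Does the approval step cover emergencies?** The procedural sentence applies whenever unblinding of an individual becomes necessary, and it carves nothing out. It cannot easily be confined to non-emergencies. The only grounds 5.1 gives for releasing an assignment outside the pharmacy are a clinical emergency and a DSMB request, and a DSMB request would not start with a site investigator. Emergencies are therefore the main case the sentence can govern.

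2. **Is there a time limit, out-of-hours cover or bypass?** None is stated in 5.1 or 7.2.

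3. **Does the approver hold the code?** The lists are:
   - 5.1: investigational pharmacists and the DSMB.
   - 5.1, paragraph on matching placebo: at the site, the unblinded pharmacist.
   - 7.2: site pharmacists only; the DCC prepares the schedule.
   - Abbreviations: the DCC, entered separately from the CCC, is described as the unblinded biostatistician.

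   The lists differ from one another, which is a separate matter. None of them includes the CCC.

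4. **What is the written path?** The investigator contacts the CCC, and the CCC approves and gives instructions. That is one request and one approval. The protocol then stops: it does not say who asks the pharmacist, who receives the assignment, or how it reaches the attending physician.

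5. **Does participant protection wait on this path?** Not as regards stopping study drug. The direction in 5.1, the discontinuation list in 5.6 and the stop points in 12.1 can all be applied blind, and none calls for CCC approval. What can be delayed is knowledge of the assignment.

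6. **Does the path itself disclose the arm to the wrong people?** No passage says that the investigator or the CCC receives it. They request, approve and instruct. The gap is that the recipient and the channel are not specified, and the investigator is the only site role named as receiving unblinding instructions.

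**The case against.** The case for leaving the text alone has four parts.

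- **The wording is advisory.** The investigator should make contact, and nothing says the pharmacist must refuse until approval arrives. A reader might infer a mandatory bar in emergencies, but the documents do not go that far. It remains true that an investigator who follows the instruction seeks approval first, and that no other route is offered.
- **Study drug can be stopped without unblinding.** This is correct, and it narrows the point. A reader might infer that emergency care itself is held up; the documents support only a delay to the code break.
- **A gatekeeper without the code protects the blind.** For elective requests this is a good argument, and the fix keeps that role. A reader might also infer bias because the investigator and the CCC know that a break is under way, given that local investigators score the chest films (3.2) and the CCC monitors the sites (8.2). The documents do not support this. Knowing that a break was requested is not knowing the arm, and 5.1 aims to limit who learns the assignment, not who knows of the event.
- **Details may be held elsewhere.** Section 11.2 cites a Manual of Operations and Procedures, which was not supplied. It is cited there for event definitions, not for unblinding. It may contain an emergency route, so the gap is shown for this document only. If it does, the unqualified approval sentence in 5.1 still conflicts with it.

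A reader might also want to express the delay as a share of hours without an approver. The documents say nothing about CCC staffing, so any such figure would only restate an assumption.

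**Conclusion.** The point holds in limited form. Section 5.1 sets out a procedure under which an emergency code break goes through approval by a body that is not a listed code holder, although the assignment is held at the site. It also leaves unstated how the assignment reaches an outside physician without passing through the investigator. The consequence is a possible delay to the code break, of unknown length. The rule applies to all participants, at most 128, but matters only for those who need an emergency break, and the documents give no basis for estimating how many.

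The conclusion assumes that the procedural sentence is followed as written and that no other document overrides it. It does not rest on any claim that blinding is already compromised or that participants cannot be taken off study drug promptly. It is a cheap improvement to the protocol, not a threat to the primary analysis.

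**What to change.** Rewrite the unblinding text in 5.1 as two cases.

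- **Clinical emergency.** The treating physician asks the site's investigational pharmacist directly. The pharmacist discloses the assignment to that physician only and records the time, reason and recipient. Afterwards the pharmacist tells the CCC that a break occurred, without the arm.
- **Any other request.** Prior CCC approval, as now. The sentence in 5.1 that lists the grounds for release should be worded to match, since it currently allows only an emergency or a DSMB request.

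List all code breaks by arm in the final report. Make the operations manual and any pharmacy instructions consistent with the new text.

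The cost is one paragraph and a log. The downside is a few breaks that the CCC might have declined; each will be recorded and can be reviewed. The change shortens the path to the code and serves 5.1's own aim of disclosing the assignment only to people outside the research who need it.

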## 5.2 Study Drug Information

### 5.2.1 Levaquin

The mechanism of action of levofloxacin and other fluoroquinolone antimicrobials involves inhibition of DNA gyrase (bacterial topoisomerase II), an enzyme required for DNA replication, transcription, repair and recombination. Levofloxacin is rapidly and essentially completely absorbed after oral administration. Peak plasma concentrations are usually attained one to two hours after oral dosing. The absolute

bioavailability of a 500 mg tablet and a 750 mg tablet of levofloxacin are both approximately 99%, demonstrating complete oral absorption of levofloxacin. Following a single intravenous dose of levofloxacin to healthy volunteers, the mean  $\pm$ SD peak plasma concentration attained was  $6.2 \pm 1.0$   $\mu\text{g/mL}$  after a 500 mg dose infused over 60 minutes and  $11.5 \pm 4.0$   $\mu\text{g/mL}$  after a 750 mg dose infused over 90 minutes. Levofloxacin oral solution and tablet formulations are bioequivalent.

Levofloxacin pharmacokinetics are linear and predictable after single and multiple oral or i.v. dosing regimens. Steady-state conditions are reached within 48 hours following a 500 mg or 750 mg once-daily dosage regimen. The mean  $\pm$ SD peak and trough plasma concentrations attained following multiple once-daily oral dosage regimens were approximately  $5.7 \pm 1.4$  and  $0.5 \pm 0.2$   $\mu\text{g/mL}$  after the 500 mg doses, and  $8.6 \pm 1.9$  and  $1.1 \pm 0.4$   $\mu\text{g/mL}$  after the 750 mg doses, respectively. The mean  $\pm$ SD peak and trough plasma concentrations attained following multiple once-daily i.v. regimens were approximately  $6.4 \pm 0.8$  and  $0.6 \pm 0.2$   $\mu\text{g/mL}$  after the 500 mg doses, and  $12.1 \pm 4.1$  and  $1.3 \pm 0.71$   $\mu\text{g/mL}$  after the 750 mg doses, respectively.

Oral administration of 500 mg levaquin with food prolongs the time to peak concentration by approximately 1 hour and decreases the peak concentration by approximately 14% following tablet and approximately 25% following oral solution administration. Therefore, levaquin tablets can be administered without regard to food.

### **Adverse Drug reactions for Levaquin**

**Common ( $\geq 3\%$ ):** in US clinical trials were nausea, headache, diarrhea, insomnia, constipation, and dizziness. An increased chance of problems with the joints and tissues around the joints has been observed in pediatric patients receiving levaquin and the safety in pediatric patients treated for more than 14 days has not been studied.

**Uncommon ( $< 3\%$ ):** tear of a tendon, increased risk of tendinitis, tendon rupture in all ages, allergic reaction, liver function problems, nervous system effects (tremors, anxiety, lightheadedness, depression, insomnia (trouble sleeping), diarrhea, nerve problems such as numbness or tingling in your hands/feet, abnormal heart rhythms, changes in your blood sugar levels, sensitivity to light, nausea, headache, constipation and dizziness.

**Rare: ( $< 1\%$ ):** prolonged the QT interval or induced Torsades de Pointes (it should not be used in patients with known prolonged QT intervals or a family history of such), increased risk of tendinitis and tendon rupture in all ages. This risk is further increased in older patients usually over 60 years of age, in patients taking corticosteroid drugs, and in patients with kidney, heart, or lung transplants [21], shortness of breath, abdominal pain, vomiting, upset stomach, rash, itching, suicidal thoughts, and swelling in your arms or legs, chest pain.

### **5.2.2 Ethambutol**

Ethambutol works by obstructing the formation of cell wall. Mycolic acids attach to the 5'-hydroxyl groups of D-arabinose residues of arabinogalactan and form mycolyl-arabinogalactan-peptidoglycan complex in the cell wall. It disrupts arabinogalactan synthesis by inhibiting the enzyme arabinosyl transferase. Disruption of the arabinogalactan synthesis inhibits the formation of this complex and leads to increased permeability of the cell wall. Ethambutol diffuses into actively growing mycobacterium cells such as tubercle bacilli. Ethambutol appears to inhibit the synthesis of one or more metabolites, thus causing impairment of cell metabolism, arrest of multiplication, and cell death. In regards to its pharmacokinetics, Ethambutol is about 75 to 80% absorbed after an oral dose. Absorption is rapid and does not seem to be affected by food.

Following a single oral dose of 25 mg/kg of body weight, ethambutol attains a peak serum level of 2 to 5  $\mu\text{g/mL}$  2 to 4 hours after administration. No drug accumulation has been observed with consecutive single daily doses of 25 mg/kg in patients with normal kidney function, although marked accumulation has been demonstrated in patients with renal insufficiency. Serum concentrations are undetectable 24 hours after

the last dose except in some patients with abnormal renal function.

Ethambutol distributes widely into body fluids and tissues. Concentrations in erythrocytes may reach 2 to 3 times the plasma concentrations. It also appears in the lungs, kidneys, urine, and saliva, and to lesser extents in pleural and ascitic fluids. Ethambutol crosses the placenta. CSF concentrations reaching 10 to 50% of serum concentrations may occur with inflamed meninges. Ethambutol is not highly bound to plasma proteins. Its volume of distribution is about 1.6 L/kg.

The half-life of ethambutol is about 3 to 4 hours in patients with normal renal function; it may be as long as 7 to 8 hours in patients with renal insufficiency and 18 to 20 hours in the anephric patient.

Within 24 hours after oral administration, approximately 50% of the initial dose is excreted unchanged in the urine, while an additional 8 to 15% appears as inactive metabolites. The main metabolic path appears to be an initial oxidation of the alcohol to an aldehydic intermediate, followed by conversion to a dicarboxylic acid. From 20 to 22% of the initial dose is excreted in the feces as unchanged drug.

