##### 4.5.2 Exclusion Criteria:

1. Inability to obtain consent
2. Age less than 18 years of age
3. Female participants of childbearing potential not willing use one of the following methods of birth control for the duration of the study and 90 days after study completion: condoms, sponge, foams, jellies, diaphragm, or non-hormonal intrauterine device, a vasectomized sole partner or abstinence. **Note: Oral contraceptive pills are not effective birth control when taking rifamycin.** Females of childbearing potential must have a negative urine pregnancy test at screening visit

4. FVC predicted value is < 45%.
5. End-stage fibrotic pulmonary disease
6. Significant underlying liver disease
7. Allergy or intolerance to any of the antibiotics within the CLEAR regimen.
8. Allergy or intolerance to albuterol
9. Poor venous access for obtaining blood samples
10. History of active tuberculosis, close contact with a person with active tuberculosis within the 6 months prior to the screening visit or has a positive PPD.
11. Significant disorder, other than sarcoidosis, that would complicate the treatment evaluation, such as respiratory, cardiac, neurologic, musculoskeletal or seizure disorders.
12. Use of an investigational drug within 30 days prior to screening or within 5 half-lives of the agent, whichever is longer.
13. Currently receiving >40mg prednisone.
14. ALT or AST  $\geq 5$  times upper limit of normal (ULN)
15. Leukopenia, as defined by WBC <3.0 cells/mm^3 or absolute neutrophil count <1000 mm^3
16. Breast feeding.
17. Color perception impairment as defined by the inability to differentiate colors per personal history or history of optic neuritis from any cause, including from sarcoidosis.
18. If patient is on immunomodulators, they must be on regimen for  $\geq 3$ -month period and on a stable dose for  $\geq 4$  weeks.
19. Family or personal history of long QT interval
20. Most recent nuclear medicine scan or echocardiogram (if done), demonstrating cardiac ejection fraction <35%
21. Participant has persistent or active infections requiring hospitalization or treatment with antibiotics, antiretrovirals, or antifungals within 30 days of baseline. Minocycline and doxycycline are not considered antibiotics when used to treat sarcoidosis.

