## 5.2.4 Rifamycins (Rifampin or Rifabutin)

### 5.2.4a Rifampin

Rifampin inhibits DNA-dependent RNA polymerase activity in susceptible cells. Specifically, it interacts with bacterial RNA polymerase but does not inhibit the mammalian enzyme. Rifampin is readily absorbed from the gastrointestinal tract. Peak serum concentrations in healthy adults and pediatric populations vary widely from individual to individual. Following a single 600 mg oral dose of rifampin in healthy adults, the peak serum concentration averages 7 mcg/mL but may vary from 4 to 32 mcg/mL. Absorption of rifampin is reduced by about 30% when the drug is ingested with food. Rifampin is widely distributed throughout the body. It is present in effective concentrations in many organs and body fluids, including cerebrospinal fluid. Rifampin is rapidly eliminated in the bile, and an enterohepatic circulation ensues. During this process, rifampin undergoes progressive deacetylation so that nearly all the drug in the bile is in this form in about 6 hours. This metabolite is microbiologically active. Intestinal reabsorption is reduced by deacetylation, and elimination is facilitated. Up to 30% of a dose is excreted in the urine, with about half of this being unchanged drug. Rifampin is about 80% protein bound. Most of the unbound fraction is not ionized and, therefore, diffuses freely into tissues. In healthy adults, the mean biological half-life of rifampin in serum averages  $3.35 \pm 0.66$  hours after a 600 mg oral dose, with increases up to  $5.08 \pm 2.45$  hours reported after a 900 mg dose. With repeated administration, the half-life decreases and reaches average values of approximately 2 to 3 hours. The half-life does not differ in patients with renal failure at doses not exceeding 600 mg daily, and consequently, no dosage adjustment is required. Following a single 900 mg oral dose of rifampin in patients with varying degrees of renal insufficiency, the mean half-life increased from 3.6 hours in healthy adults to 5.0, 7.3, and 11.0 hours in patients with glomerular filtration rates of 30 to 50 mL/min, less than 30 mL/min, and in anuric patients, respectively.

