### **5.3 Study Drug Dosing and Administration:**

The following oral CLEAR medications or matching placebo will be introduced as follows:

Day 0 Start: Azithromycin: 250mg po QD (or 500 3 days/week if toxicity) x 8 weeks *and*  
Ethambutol: 1200 mg po QD for  $\geq 50$ kg; <50kg 800 mg po QD (or 3 days/week if toxicity) x 8 weeks  
Rifampin 600 mg QD or Rifabutin 300mg po QD (or 3 days/week if toxicity) x 16 weeks  
Levaquin: 500 mg po QD (or 3 days/week if toxicity) x 16 weeks

Participants will be allowed to take their regimen three times/week instead of daily (which has been shown to be equally efficacious) if toxicity occurs that is thought to be drug related. In addition, if toxicity warrants, one or more drugs can be discontinued and the participant can continue to participate.

The site PI may also elect to stagger the start of study drugs to help identify which drugs may be eliciting which side effects. The study drugs would be introduced starting with Azithromycin and Ethambutol at the baseline visit (day 0) and introducing Rifampin (or Rifabutin) the following week (day 7), and Levaquin one week later (day 14) using the same dosages as above.

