#### **5.6 Discontinuation of Study Drug Administration**

Treatment will continue for a maximum of 112 doses after study enrollment or 16 weeks post-randomization, whichever comes first. Treatment will be discontinued in the following circumstances:

1. Death
2. Primary care provider or participant request
3. ALT is noted to exceed ten times the upper limit of normal
4. A serious adverse event has occurred and is thought to be related to study drug and in the opinion of the investigator or attending physician warrants discontinuation of the study drug, or any intolerable or unacceptable adverse event (including clinically significant abnormal labs thought to be due to study drug) that in the opinion of the investigator or attending physician warrants discontinuation
5. Positive pregnancy test
6. Non-compliance with the regimen and timing that might result in dropping out from the study

7. Development of an intolerable AE due to study participation as determined by the Investigator, participant, or both.
8. Development of an intercurrent illness, condition, or procedural complication, which would interfere with the participant's continued participation.

Participants who have stopped taking study drugs may continue to participate in the study and will follow the appropriate procedures in the protocol.

Any participant who discontinues treatment for medical reasons, e.g. because of adverse events (AEs) or clinical laboratory abnormalities, should be followed up at medically appropriate intervals in order to evaluate the course and to ensure reversibility or stabilization of the abnormality or event. If a participant fails to return for a scheduled visit, a documented effort must be made to determine the reason. This information should be recorded in the study records.

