### 6.1 Screening Visit 1 Assessments

- Consent Participant
- Demographic and Enrollment Data
- Pertinent Medical History (including comorbidities and current medication list)
- Physical Examination (including height, weight and gender)
- Urine Pregnancy Test (if female of childbearing potential)
- Screening Labs; Complete Metabolic Panel (CMP) including: sodium, potassium, HCO3, creatinine, glucose, calcium, BUN, total bilirubin, total protein, ALT, AST\*
- Complete Blood Cell Count including: WBC, RBC, hemoglobin, hematocrit and platelet count\*
- Immune responses against mycobacterial ESAT-6 (T cell recognition assay)  
\*If this testing was done within the 14 days prior to this visit, these results may be used for this visit.

A screening log will be maintained for those potential participants who are contacted for screening in this study. This log will include the reason if the patient is not enrolled. Data entry into REDCap of screening log data will not include patient identifiers. Clinical sites will maintain the screening log in their research files.

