## **11. Adverse Event Reporting**

Investigators will determine if any clinical adverse experiences occur during the period from enrollment through study month 6 or hospital discharge or death, whichever occurs first. The investigator will evaluate any changes in laboratory values and physical signs and will determine if the change is clinically important and different from what is expected in the course of treatment of patients with sarcoidosis. If clinically important and unexpected adverse experiences occur, they will be recorded on the adverse event case report form.

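### Ethambutol's starting dose depends on weight band alone, and no stated rule uses the creatinine already measured, although the protocol reports marked accumulation in renal insufficiency

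*Combined protocol and SAP*

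**What the plan says.** **Pharmacology (section 5.2.2).** With daily doses of 25 mg/kg and normal kidneys no accumulation is seen, "although marked accumulation has been demonstrated in patients with renal insufficiency". The half-life is given as about 3 to 4 hours normally, up to 7 to 8 hours in renal insufficiency, and 18 to 20 hours without kidneys. Absorption is 75 to 80%, and "approximately 50% of the initial dose is excreted unchanged in the urine" within 24 hours.

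**Dose (section 5.3).** Participants of 50 kg or more receive 1200 mg daily. For lighter participants the entry reads "<50kg 800 mg po QD (or 3 days/week if toxicity) x 8 weeks". The thrice-weekly schedule is open only after toxicity.

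**Measurement.** The screening panel in section 6.1 includes "creatinine, glucose, calcium, BUN, total bilirubin, total protein, ALT, AST". Sections 6.4 to 6.6 and the schedule in Appendix A repeat the metabolic profile at weeks 4, 8 and 16.

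**Rules that use laboratory values.** Section 4.5.2 limits ALT/AST (exclusion 14) and white cell or neutrophil count (exclusion 15), and names liver disease (exclusion 6). The only numeric laboratory stop is ALT above 10 times ULN (sections 5.6, 9.4 and 12.1). None of these rules is renal.

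**The contrast with rifampin (section 5.2.4a).** There the renal question is raised and answered: "The half-life does not differ in patients with renal failure at doses not exceeding 600 mg daily, and consequently, no dosage adjustment is required".

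**The concern.** The protocol identifies a renal hazard for one of its four drugs and collects the test that would detect it, but never connects the two. Followed as written, it starts full-dose ethambutol in a participant whose raised creatinine is already on the screening report, and offers a lower dose only once toxicity has appeared. Section 4.5.3 explains that exclusions exist partly to avoid drug toxicity, so a renal limit would fit the protocol's own reasoning.

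At stake is avoidable over-exposure in individual participants. There is a second route to it: section 5.4.1 makes ethambutol the second-choice replacement in the two-drug phase, so some participants could receive it again after week 8.

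**Working it through.** The plan states no figure on this point, so there is none to reproduce. The check has three parts: which clauses could act, how far exposure might rise, and how long it would last.

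**1. Clauses that could act on a raised creatinine**

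- Exclusion 11 covers disorders "that would complicate the treatment evaluation, such as respiratory, cardiac, neurologic, musculoskeletal or seizure disorders". The list is illustrative, but it omits renal disease, and the test is interference with evaluation.
- Exclusion 22 covers significant findings in the history or on physical or psychiatric examination that the investigator thinks affect safety. Known renal disease is history, so it can be caught here. A laboratory value seen for the first time at screening is not named.
- Section 11: "The investigator will evaluate any changes in laboratory values and physical signs". Stable impairment shows no change.
- Section 5.6, item 4 allows stopping for intolerable events, "including clinically significant abnormal labs thought to be due to study drug". Pre-existing impairment is not due to study drug.

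No clause requires action for stable impairment visible only on the panel.

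**2. Exposure, by two rough routes from section 5.2.2**

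*Half-life route.* Assuming unchanged volume and absorption, the exposure ratio equals the half-life ratio.
- Mid-range: 7.5/3.5 = 2.1. Bounds: 7/4 = 1.75 and 8/3 = 2.7.
- Carry-over with once-daily dosing is 1/(1 − 2^(−24/t)): 1.00 to 1.02 at 3 to 4 h, and 1.10 to 1.14 at 7 to 8 h. Most of the excess is therefore longer exposure after each dose, with little build-up from day to day.

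*Excretion route.* The renal share of absorbed drug is fe = 0.50/0.80 = 0.625 to 0.50/0.75 = 0.667. With renal clearance at fraction r of normal, the exposure ratio is 1/(1 − fe(1 − r)). Creatinine is assumed to vary as 1/r.

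| Creatinine relative to normal | r | Exposure ratio |
|---|---|---|
| 1.5 | 0.67 | 1.26–1.29 |
| 2 | 0.50 | 1.45–1.50 |
| 4 | 0.25 | 1.88–2.00 |

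*Do the routes agree?* Not at the extreme. With r = 0 the excretion route is capped at 1/(1 − fe) = 2.7 to 3.0, while the half-life without kidneys gives 18/4 = 4.5 to 20/3 = 6.7. At least one assumption fails, so both sets of figures are rough guides. To reach 2.14 by the excretion route, r must be about 0.15 to 0.20, that is, creatinine about 5 to 7 times normal.

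*Dose per kg.* 1200/50 = 24, 1200/60 = 20, 1200/80 = 15 and 1200/100 = 12 mg/kg. The 800 mg dose reaches 25 mg/kg only at 800/25 = 32 kg. For participants of 32 kg or more, the bands therefore do not exceed the level at which section 5.2.2 reports no accumulation with normal kidneys.

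**3. Duration**

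Planned ethambutol is 8 × 7 = 56 days. Section 5.2.2 says optic neuropathy has not been reported with under 90 days of therapy. If the drug is resumed under 5.4.1 on day d and continued to day 112, the total is 56 + (112 − d), which reaches 90 when d is 78 or earlier.

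**The case against.** The strongest reply is that investigator judgement already covers most of this. Comorbidities are recorded at screening, exclusion 22 is broad, and an investigator who considers renal disease unsafe must exclude the patient. That stands for known disease, and it narrows the gap to impairment first seen on the panel or known impairment that the investigator does not act on.

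Section 9.1 says that the doses follow current FDA recommendations, and section 11.2 cites a Manual of Operations and Procedures. The first is not a renal rule. The second was not supplied and might contain one.

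The size is also open to challenge, and rightly. A doubling of exposure corresponds, by the excretion route, to impairment that few investigators would miss. At 1.5 times normal creatinine, where a patient could plausibly slip through, the estimate is about 1.3 times. Body weight offsets part of it: at 1.5 times exposure, 1200 mg matches normal-kidney exposure to 25 mg/kg at 1200 × 1.5/25 = 72 kg, and falls below it in heavier participants. Section 5.2.2 does not establish 25 mg/kg as safe in renal disease, so this limits the gap without closing it.

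A reader might infer that the plan exposes participants with renal impairment to optic nerve damage. The documents do not support that. They list optic neuritis as a rare reaction to ethambutol but link accumulation to no specific toxicity, and planned treatment is shorter than 90 days. Only re-use under 5.4.1 could pass that mark.

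**Conclusion.** The point holds as a modest participant-safety gap. In the supplied documents the starting dose of ethambutol ignores renal function, and no entry, dosing or numeric stop rule uses a creatinine that is collected four times.

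Exposure in an affected participant would exceed normal by an uncertain amount: about 1.3 to 1.5 times for creatinine 1.5 to 2 times normal, or 1.75 to 2.7 times from the half-lives. These figures rest on constant volume, on 24-hour urinary excretion as the renal share, and on creatinine varying inversely with clearance. The number of participants concerned is not given and cannot be estimated.

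Two further readings go too far. The weight bands are not shown to overdose people with normal kidneys. The FVC comparison and its sample size are not affected.

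**What to change.** Add one exclusion to section 4.5.2 (and to the synopsis list): screening creatinine above a stated multiple of ULN, in the form of exclusion 14. Limits of 1.5 or 2 times ULN are examples. If ULN is taken as normal function, they correspond to roughly 1.3 and 1.5 times normal exposure by the excretion route. The sponsor's safety lead should set the final value.

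Add one check. Compare the week 4 creatinine with the same limit before ethambutol or its matching placebo is continued, and compare the latest creatinine before any re-use under section 5.4.1. Stop that component if the limit is exceeded. The week 8 value matters mainly for re-use, because scheduled ethambutol ends then. The rule must be identical in both arms so that the blind holds.

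If the Manual of Operations and Procedures already contains a renal rule, moving it into the protocol would suffice.

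The cost is two lines of text, using a test already collected, and a few more screen failures.
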